5.1.5 Accountability and dispensation

Administration will occur at the study site (Winship Cancer Institute) or Grady Memorial Hospital and recorded in medical record as well as study specific event sheet.

5.1.6 Disposition of unused investigational study drug

Each site will account for all investigational study drug dispensed and also for appropriate destruction. Certificates of delivery and destruction must be signed

5.2 Sirolimus

5.2.1 Formulation/packaging/storage

Sirolimus (Rapamune) is supplied as in both an oral solution and tablets for oral administration. This study will preferentially use the tablet formulation from commercial supply:

Rapamune Tablets are available supplied in bottle or blister cards as follows:

- NDC 0008-1040-05, 0.5 mg, tan, triangular-shaped tablets marked “RAPAMUNE 0.5 mg” on one side; bottle containing 100 tablets.
- NDC 0008-1040-10, 0.5 mg, tan, triangular-shaped tablets marked “RAPAMUNE 0.5 mg” on one side; in of 100 tablets (10 blister cards of 10 tablets each).
- NDC 0008-1041-05, 1 mg, white, triangular-shaped tablets marked “RAPAMUNE 1 mg” on one side; bottle containing 100 tablets.
- NDC 0008-1041-10, 1 mg, white, triangular-shaped tablets marked “RAPAMUNE 1 mg” on one side; in of 100 tablets (10 blister cards of 10 tablets each).
- NDC 0008-1042-05, 2 mg, yellow-to-beige triangular-shaped tablets marked “RAPAMUNE 2 mg” on one side; bottle containing 100 tablets.

Rapamune Tablets should be stored at 20° to 25°C [USP Controlled Room Temperature] (68° to 77°F). Use cartons to protect blister cards and strips from light. Dispense in a tight, light-resistant container as defined in the USP.

Clinical Study Protocol

Investigational Drug Substance: MEDI4736 Sirolimus (Rapamune)

Study Number **19-20015**

Edition Number: **4**

Date: **11 February 2022**

5.2.2 Doses and treatment regimens

The dose of sirolimus for this study is 6mg orally daily once on day 1, followed by 2mg orally daily from day 2 through 21.

5.2.3 Dose administration

Patients will self-administer on a continuous once daily dosing schedule. Patients should be instructed to take the dose of sirolimus daily in the morning with or without food at approximately the same time each day. However, dietary habits around the time of sirolimus intake should be as consistent as possible throughout the study. Patients should swallow the tablets as a whole and not chew them.

If vomiting occurs during the course of treatment, no re-dosing of the patient is allowed before the next scheduled dose. The occurrence and frequency of any vomiting during a treatment cycle must be noted as an adverse event. If the patient forgets to take her/his dose and does not remember before 6:00 PM, then the dose should be withheld that day and sirolimus resumed the following day.

Patients must avoid consumption of St. John's Wort, Seville oranges, grapefruit or grapefruit juice, grapefruit hybrids, pummelos and exotic citrus fruits from 7 days prior to the first dose of study medication and during the entire study treatment period due to potential CYP3A4 interaction with the study medication. Patients must avoid concomitant intake of strong and moderate CYP3A4/5 inhibitors and inducers. Orange juice is allowed.

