Cases of interstitial lung disease [ILD] (including pneumonitis, bronchiolitis obliterans organizing pneumonia [BOOP], and pulmonary fibrosis), some fatal, with no identified infectious etiology have occurred in patients receiving immunosuppressive regimens including Rapamune. In some cases, the ILD was reported with pulmonary hypertension (including pulmonary arterial hypertension [PAH]) as a secondary event. In some cases, the ILD has resolved upon discontinuation or dose reduction of Rapamune. The risk may be increased as the trough sirolimus concentration increases.

Additional risks that pertain to the renal transplant population include declines in renal function, proteinuria, increased risk of calcineurin associated thrombotic microangiopathy, and additional opportunistic infections such as PCP and latent viral infections with BK or others. Please refer to full prescribing information in the FDA package insert.

Absorption

“The mean time to peak concentration after ingestion of the oral solution is approximately 1 hour and 2 hours in healthy subjects and renal transplant patients, respectively. The systemic availability of sirolimus is low, and was estimated to be approximately 14% after the administration of Rapamune Oral Solution. In healthy subjects, the mean bioavailability of sirolimus after administration of the tablet is approximately 27% higher relative to the solution. Sirolimus tablets are not bioequivalent to the solution; however, clinical equivalence has been demonstrated at the 2 mg dose level. To minimize variability in sirolimus concentrations, both Rapamune Oral Solution and Tablets should be taken consistently with or without food.”

Distribution

“The mean (\pm SD) blood-to-plasma ratio of sirolimus was 36 ± 18 in stable renal allograft patients, indicating that sirolimus is extensively partitioned into formed blood elements. The mean volume of distribution (V_{ss}/F) of sirolimus is 12 ± 8 L/kg. Sirolimus is extensively bound (approximately 92%) to human plasma proteins, mainly serum albumin (97%).”

Metabolism

“Sirolimus is a substrate for both CYP3A4 and P-gp. Sirolimus is extensively metabolized in the intestinal wall and liver and undergoes counter-transport from enterocytes of the small intestine into the gut lumen. Inhibitors of CYP3A4 and P-gp increase sirolimus concentrations. Inducers of CYP3A4 and P-gp decrease sirolimus concentrations.”

Excretion

Date: **11 February 2022**

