10. Active infection including **tuberculosis** (clinical evaluation that includes clinical history, physical examination and radiographic findings, and TB testing in line with local practice), **hepatitis B** (known positive HBV surface antigen (HBsAg) result), **hepatitis C**. Patients with a past or resolved HBV infection (defined as the presence of hepatitis B core antibody [anti-HBc] and absence of HBsAg) are eligible. Patients positive for hepatitis C (HCV) antibody are eligible only if polymerase chain reaction is negative for HCV RNA.

11. Current or prior use of immunosuppressive medication within 14 days before the first dose of durvalumab. The following are exceptions to this criterion:

- a. Intranasal, inhaled, topical steroids, or local steroid injections (e.g., intra articular injection)
- b. Systemic corticosteroids at physiologic doses not to exceed 10 mg/day of prednisone or its equivalent
- c. Steroids as premedication for hypersensitivity reactions (e.g., CT scan premedication)

12. Receipt of live attenuated vaccine within 30 days prior to the first dose of IP. Note: Patients, if enrolled, should not receive live vaccine whilst receiving IP and up to 30 days after the last dose of IP.

13. Female patients who are pregnant or breastfeeding or male or female patients of reproductive potential who are not willing to employ effective birth control from screening to 90 days after the last dose of durvalumab monotherapy.

14. Known allergy or hypersensitivity to any of the study drugs or any of the study drug excipients.

Clinical Study Protocol

Investigational Drug Substance: MEDI4736 Sirolimus (Rapamune)

Study Number **19-20015**

Edition Number: 4

Date: **11 February 2022**

15. Prior randomisation or treatment in a previous durvalumab clinical study regardless of treatment arm assignment.
16. Patients with a history of idiopathic pulmonary fibrosis, pneumonitis (including drug induced), organizing pneumonia, or evidence of active pneumonitis on screening chest CT scan
17. Inability to stop prohibited concomitant medications listed in Section 7.7.2.
18. Judgment by the investigator that the patient is unsuitable to participate in the study and the patient is unlikely to comply with study procedures, restrictions and requirements.

Procedures for withdrawal of incorrectly enrolled patients are presented in Section 4.3

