Herbal and natural remedies which may have immune-modulating effects	Should not be given concomitantly unless agreed by the sponsor
Seville orange, star fruit, grapefruit and their juices	Should not be used concomitantly as they affect P450 and P glycoprotein (P-gp) activity.
Strong inhibitors of CYP3A4 or P-GP	Should not be given concomitantly, see table 5
Strong inducers of CYP3A4	Should not be given concomitantly, see table 5
Moderate CYP3A4 inhibitors	Should be used with caution, see table 5

Table 6. List of CYP3A4 strong and moderate inhibitors and inducers

Strong CYP3A4,5,7 inhibitors	Moderate CYP3A4,5,7 inhibitors	CYP3A4 inducers
clarithromycin	aprepitant	Barbiturates
Conivaptan	atazanavir	Carbamazepine
grapefruit juice	cimetidine	Efavirenz
Indinavir	ciprofloxacin	Modafenil
Itraconazole	darunavir	Nevirapine
Ketoconazole	diltiazem	Oxcarbazepine
Lopinavir	erythromycin	Phenobarbital
Mibepradil	fluconazole	Phenytoin
Nefazodone	tofisopam	pioglitazone
Nelfinavir	verapamil	Rifabutin
Posaconazole	amprenavir	Rifampin
Ritonavir	fosamprenavir	St. John's wort
Saquinavir		Topiramate

Clinical Study Protocol

Investigational Drug Substance: MEDI4736 Sirolimus (Rapamune)

Study Number **19-20015**

Edition Number: 4

Date: **11 February 2022**

Strong CYP3A4,5,7 inhibitors	Moderate CYP3A4,5,7 inhibitors	CYP3A4 inducers
Telithromycin		troglitazone
Troleandomycin		
Voriconazole		

This database of CYP inhibitors was compiled from the Indiana University School of Medicine's "Clinically Relevant" Table and from the University of Washington's Drug Interaction Database based on in vitro studies. Strong inhibitors are predicted to increase BKM120 AUC $>$ 5-fold, and moderate inhibitors are predicted to increase BKM120 AUC \geq 2-fold but $<$ 5-fold.
 
This database of CYP inducers was compiled from the FDA's "Guidance for Industry, Drug Interaction Studies;" from the Indiana University School of Medicine's "Clinically Relevant" Table; and from (Pursche et al. 2008).
		

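### Section 5.2.3 bars moderate CYP3A4 inhibitors with sirolimus, Table 5 allows them with caution, and 12 listed drugs are left with conflicting instructions

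*Combined protocol and SAP*

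**What the plan says.** Section 5.2.3, on how sirolimus is taken, sets a rule with no stated exception: "Patients must avoid concomitant intake of strong and moderate CYP3A4/5 inhibitors and inducers". An adjacent sentence gives St. John's wort and the interacting citrus fruits a time window, "from 7 days prior to the first dose of study medication and during the entire study treatment period". The sentence on drugs has none.

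Table 5 in Section 7.2.2 is titled as a list of prohibited medications. Its rows for strong inhibitors of CYP3A4 or P-gp and for strong CYP3A4 inducers say that these are not to be given. Its row for moderate CYP3A4 inhibitors says "Should be used with caution, see table 5". The inducer row covers only "Strong inducers of CYP3A4". The drugs themselves are in the next table, Table 6, "List of CYP3A4 strong and moderate inhibitors and inducers". That table separates strong from moderate inhibitors but puts all inducers in one ungraded column.

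Exclusion criterion 17 in Section 4.2 reads "Inability to stop prohibited concomitant medications listed in Section 7.7.2".

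On pharmacology, Section 1.6.2.2 says "Inhibitors of CYP3A4 and P-gp increase sirolimus concentrations", and of interstitial lung disease it says "The risk may be increased as the trough sirolimus concentration increases". Section 3.1 rules out dose changes for individual patients.

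**The concern.** Two current sections give different orders for the same drugs. A site that keeps moderate inhibitors away from sirolimus satisfies both. A site that follows Table 5 and gives one with caution breaches Section 5.2.3. No visible text ranks the two.

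Two things are at stake. One is dosing safety: sirolimus is given at a fixed dose, so keeping interacting drugs out is a main control on exposure, and the lung toxicity that the protocol links to trough is also a durvalumab event of special interest (Section 10.2.3) and, for pneumonitis, a dose-limiting toxicity criterion (Section 6.3). The other is consistent enrolment: two sites could decide differently about a patient who cannot stop, say, diltiazem.

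**Working it through.** This is a comparison of texts. No sample size, power or error rate enters.

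**1. The rules side by side**

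| Drug class | Section 5.2.3 | Table 5 |
|---|---|---|
| Strong CYP3A4 inhibitors | avoid | not to be given |
| Moderate CYP3A4 inhibitors | avoid | use with caution |
| Strong CYP3A4 inducers | avoid | not to be given |
| Moderate CYP3A4 inducers | avoid | not mentioned |

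The second row is a direct conflict. The fourth is a lesser gap: Table 5 is silent, and the ungraded inducer column of Table 6 can be read as barring every drug in it.

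**2. How many drugs are affected**

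- Moderate-inhibitor column of Table 6: aprepitant, atazanavir, cimetidine, ciprofloxacin, darunavir, diltiazem, erythromycin, fluconazole, tofisopam, verapamil, amprenavir, fosamprenavir. That is 12 drugs with conflicting instructions.
- Inducer column: 14 entries. St. John's wort is barred by name in Section 5.2.3, so the Table 5 status of 14 − 1 = 13 depends on how the ungraded column is read.

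**3. What exclusion 17 turns on**

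The criterion refers only to drugs listed in one section. Section 7.7.2 does not exist, and the list is in Section 7.2.2. Section 5.2.3 therefore does not feed this criterion. The eligibility doubt arises inside Table 5: the title says prohibited, while the row says caution.

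**4. What monitoring can catch during dosing**

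The last sirolimus dose is on day 21 (Section 5.2.2). The one scheduled level is on day 22 (Section 8.2.3, on sirolimus levels) or day 23 (Section 8.1.2, which stores it for batch analysis). Scheduled levels within days 1 to 21: 0. The section on blood volumes allows additional draws, but none is scheduled.

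**5. How long a bar needs to last**

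- Lead-in of 7 days plus 21 days of dosing = 28 days, about 4 weeks.
- Section 1.6.2.2 gives a half-life of about 62 hours, in stable renal transplant patients. Taking five half-lives as a conventional washout (an assumption), 5 × 62 = 310 hours, and 310 / 24 = 12.9 days, which runs to about day 34.
- The Schedule of Study Assessments puts the pre-surgery visit at days 57 to 64, and Section 8.1.3 defines end of treatment as the 30-day visit after surgery or discharge. A bar running through study treatment could thus outlast sirolimus by weeks.

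**The case against.** Several safeguards exist. Section 7.2 requires all concomitant drugs to be recorded and the principal investigator to be alerted to agents acting on CYP450. Section 6.4.2 provides for interruption on toxicity, and extra levels can be drawn. These limit the risk. They do not say whether a patient on a moderate inhibitor may be enrolled and dosed.

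Appendix 4, to which Section 7.2 refers for interacting drugs, was not available. It might state a working rule, so the practical effect is less certain than the mismatch itself. It could not make Section 5.2.3 and Table 5 agree.

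Either rule alone would end the conflict, so the choice of the stricter one is a judgement. It is proposed because doses are not adjusted individually and no level is scheduled while the drug is being taken.

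A reader might go further and treat 15 ng/mL, the top of the range in Section 3.1, as a ceiling: from the cited median trough of 6.8 ng/mL, a rise of 15 / 6.8 = 2.2-fold would pass it. The documents do not support that as a measure of harm. Section 3.1 ties the 5 to 15 ng/mL range to memory T-cell proliferation in pre-clinical work. Sections 1.3 and 1.5.1.5 cite goal troughs of 12 to 20 ng/mL in approved use, and a 21-day window trial, described as well tolerated, that lowered the dose only above 20 ng/mL. Nor do the documents size the effect of moderate inhibitors on sirolimus: the fold-changes under Table 6 are for a different compound, BKM120.

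**Conclusion.** The inconsistency is real and should be corrected. Twelve named drugs are to be avoided in one section and used with caution in another. Their status under exclusion 17 is unclear because a caution row sits in a table titled as prohibited. The inducer wording is a lesser ambiguity. It would be too strong to say that Table 5 expressly permits moderate inducers, since it is silent on them.

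The point rests on the current text of Sections 4.2, 5.2.3 and 7.2.2, with Appendix 4 unseen. It is an operational safety matter. No size of effect on sirolimus exposure is claimed, and nothing here changes the sample size, the analysis method or the two-stage decision rule.

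**What to change.** - Change the moderate-inhibitor row of Table 5 to say that these drugs should not be given concomitantly with sirolimus, matching Section 5.2.3.
- Make the inducer row cover strong and moderate inducers.
- State one window in both places, tied to sirolimus exposure: a lead-in before day 1 (for example the 7 days already used for interacting foods) through the last dose on day 21, with any short washout the sponsor chooses. Do not extend it through surgery or the end-of-treatment visit. The list includes ciprofloxacin, erythromycin, fluconazole, diltiazem and verapamil, which may be needed around an operation, and Table 4 supports antibiotics where necessary.
- Point the Table 5 rows to Table 6 and exclusion 17 to Section 7.2.2, and check that Appendix 4 agrees.

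The cost is protocol wording, since concomitant drugs are already recorded. The downside is that patients who cannot stop or switch such a drug for about 4 weeks, or longer if a washout is added, become ineligible. A patient who comes to need one during days 1 to 21 would need an alternative drug or a sirolimus interruption. The documents do not say how many patients that would be.

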5.2.4 Monitoring of dose administration

The patient will be requested to maintain a medication diary of each dose of medication. The medication diary will be returned to clinic staff at the end of each course.

5.2.5 Disposition of unused investigational study drug

Patients will return any unused medication to their study site for disposal by investigational pharmacy services.

5.3 Heavy Water (D2O)

Deuterated water is 70% D2O and 30% normal H2O and is manufactured and supplied by Cambridge Isotope Laboratories. The Emory research pharmacy will steriley portion out individually labeled 50ml conical tubes and provide to trial patients who agree to optional heavy water labelling study. Patients will self-administer 50 ml orally TID for the first 5 days to serve as

Clinical Study Protocol

Investigational Drug Substance: MEDI4736 Sirolimus (Rapamune)

Study Number **19-20015**

Edition Number: 4

Date: **11 February 2022**

a loading dose (Day 22, C1 Durvalumab). Subsequently, patients will self-administer 50 ml orally BID from day 27 until the day prior to surgery. Previous and ongoing studies have shown high compliance among donors. Since compliance with drinking the heavy water is critical to achieve adequate deuterium enrichment of body water, participants will be encouraged and rewarded for completing the memory aid provided (See **Appendix 5**) to help keep track of the heavy water consumption.

6. TREATMENT PLANT

6.1 Patient enrollment

Patients will be enrolled following screening procedures on the open label study. Those patients who withdraw consent and discontinue the study prior to a dose of durvalumab will be replaced.

6.2 Dosage and administration

Refer to Section 5.1.4 and 5.1.5 for the administration and monitoring of administration of durvalumab

Refer to Section 5.2.3 and 0 for the administration and monitoring of any additional study drug(s)

6.3 Definition of DLT

Dose-limiting toxicities (DLTs) will be evaluated in the first 6 patients enrolled on the trial. The period for evaluating DLTs will be from the time of first administration of durvalumab until discharge from the hospital following surgical resection. Grading of DLTs will follow the guidelines provided in the Common Terminology Criteria for Adverse Events (CTCAE) version 5.0. Continued enrollment of subsequent patients will be allowed during the DLT monitoring period.

If and when ≥ 2 DLTs are identified in the first 6 patients, then subsequent enrollment will be halted until safety review. Patients already started on therapy will continue per protocol.

A DLT is defined as the occurrence of an adverse event (AE) that is **at least possibly related to the investigational product (IP) or investigational regimen (IR)**, with two exceptions: any grade of vitiligo or alopecia will not qualify as a DLT. AEs that are **at least possibly related to durvalumab-containing regimens** shall be assessed as DLTs if they meet any of the following criteria:

Hematologic toxicity:

Date: **11 February 2022**

- Grade ≥ 3 neutropenia complicated by fever $>38.3^{\circ}\text{C}$
- Grade 4 neutropenia (lasting more than 7 days)
- Grade ≥ 3 thrombocytopenia with significant bleeding
- Grade 4 thrombocytopenia (regardless of duration)
- Grade 4 anemia (regardless of duration)

Non-hematologic toxicity:

- Any Grade 4 non-immune-mediated AE
- Any Grade 4 immune-mediated AE, excluding endocrinopathies
- Any Grade 3 non-immune mediated AE that does not resolve to \leq Grade 1 or baseline within 30 days with optimal medical management
- Any Grade 3 immune-mediated AE – excluding diarrhea/colitis, pneumonitis, hepatitis, rash, neurotoxicity, myocarditis, myositis/polymyositis, endocrinopathies and nephritis – that does not resolve to \leq Grade 1 or baseline within 30 days after onset of the event despite optimal medical management including systemic corticosteroids
- Grade 3 diarrhea or colitis that does not resolve to \leq Grade 1 within 14 days
[*both* immune- *and* non-immune-mediated indicated here; the same is the case if not specified in remaining bullet points below]
- Grade 3 noninfectious pneumonitis
- Grade 2 noninfectious pneumonitis that does not resolve to \leq Grade 1 within 3 days of the initiation of maximal supportive care
- **Aspartate aminotransferase (AST) or alanine aminotransferase (ALT) $\geq 3 \times$ ULN** with concurrent increase in total bilirubin (TBL) $\geq 2 \times$ ULN without evidence of cholestasis or alternative explanations (e.g., viral hepatitis, disease progression in the liver; i.e., “Hy’s Law”)
- ALT or AST $> 8 \times$ ULN or TBL $> 5 \times$ ULN
- Grade 3 immune-mediated rash that does not resolve to \leq Grade 1 or baseline within 30 days
- Grade 2 rash covering $> 30\%$ BSA that does not resolve to \leq Grade 1 or baseline within 30 days
- Any grade of immune-mediated rash with bullous formation
- Grade 3 immune-mediated neurotoxicity (excluding Guillain-Barre and myasthenia gravis) that does not resolve to \leq Grade 1 within 30 days
- Grade 2 or 3 immune-mediated peripheral neuromotor syndrome (such as Guillain-Barre and myasthenia gravis) that does not resolve to \leq Grade 1 within 30 days or that exhibits signs of respiratory insufficiency or autonomic instability
- Grade 3 immune-mediated myocarditis
- Any symptomatic immune-mediated myocarditis that does not become asymptomatic within 3 days of initiating optimal medical management including systemic corticosteroids

- Grade 2 or 3 immune-mediated myositis/polymyositis that does not resolve to Grade ≤ 1 within 30 days of initiating optimal medical management including systemic corticosteroids or that exhibits signs of respiratory insufficiency regardless of optimal medical management
- Immune-mediated increase in creatinine $>3 \times$ ULN, or $>3 \times$ baseline for patients with a baseline creatinine elevated above ULN
- Delay in administration of scheduled doses of sirolimus greater than 2 weeks because of drug-related toxicity of any grade.

Any treatment-related toxicities that first occurred during the DLT period must be followed for resolution to determine if the event qualifies as a DLT as specified in the DLT criteria above.

Immune-related AEs are defined as AEs of an immune nature (i.e., inflammatory) in the absence of a clear alternative etiology. In the absence of a clinically significant abnormality, repeat laboratory testing will be conducted to confirm significant laboratory findings prior to designation as a DLT.

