3.4 Study oversight for safety evaluation

There will be a planned safety assessment of the first 6 patients, who will be monitored through hospital discharge following surgical resection to assess for dose limiting toxicities (DLTs) related to sirolimus followed by durvalumab therapy. If $\geq 2/6$ patients have a DLT then additional enrollment will be halted until safety assessment is completed.

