4.4 Replacement of patients

Patients who withdraw consent prior to administration of durvalumab will be replaced. Patients who discontinue study treatment prematurely will not be replaced.

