6.4.2 Sirolimus

Table 2 Criteria for interruption and re-initiation of Sirolimus

Stomatitis	Description	Management/Next Dose for Sirolimus
Grade 1	Minimal symptoms, normal diet	No modifications necessary. Manage with non-alcoholic or salt water (0.9%) mouth wash several times a day
Grade 2	Symptomatic but can eat and swallow modified diet	Manage with topical analgesic mouth treatments (e.g. benzocaine, menthol or phenol) with or without topical corticosteroids (i.e. triamcinolone oral paste)
Grade 3	Symptomatic and unable to adequately aliment or hydrate orally	Temporary dose interruption until recovery to grade ≤ 1 . Manage with topical analgesic mouth treatments (e.g. benzocaine, menthol or phenol) with or without topical corticosteroids (i.e. triamcinolone oral paste)
Grade 4	Symptoms associated with life-threatening consequences	Discontinue Sirolimus and treat with appropriate medical therapy.

*Patients requiring a delay of >2 weeks should go off protocol therapy.

Other Non-hematologic toxicities	Management/Next Dose for Sirolimus
\leq Grade 1	If toxicity is tolerable, no dose adjustment required. Initiate appropriate medical therapy and monitor.
Grade 2	If toxicity is tolerable, no dose adjustment required. Initiate appropriate medical therapy and monitor. If toxicity becomes intolerable, temporary dose interruption until recovery to grade ≤ 1 . Re-initiate sirolimus at the same dose. If toxicity recurs at grade 2, interrupt sirolimus until recovery to grade ≤ 1 . Re-initiate sirolimus at the same dose.

Other Non-hematologic toxicities	Management/Next Dose for Sirolimus
Grade 3	Temporary dose interruption until recovery to grade ≤ 1 . Initiate appropriate medical therapy and monitor. Consider re-initiating sirolimus. If toxicity recurs at grade 3, consider discontinuation.
Grade 4	Discontinue sirolimus and treat with appropriate medical therapy.

*Patients requiring a delay of >2 weeks should go off protocol therapy.

Hematologic Toxicities (anemia, neutropenia, thrombocytopenia)	Management/Next Dose for Sirolimus
\leq Grade 1	No change in dose
Grade 2	Hold until \leq Grade 1. Resume at same dose.
Grade 3	Hold until $<$ Grade 2. Resume at same dose. *
Grade 4	Off protocol therapy

* Patients who develop grade 3 neutropenia associated with temperature higher than 38.3 C should go off protocol therapy. Patients requiring a delay of >2 weeks should go off protocol therapy

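### The DLT window opens at the first durvalumab dose, so the sirolimus-delay criterion has essentially no effect and lead-in toxicity is not clearly counted in the 2-of-6 halt rule or the DLT rate

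*Combined protocol and SAP*

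**What the plan says.** - **Window (6.3).** "The period for evaluating DLTs will be from the time of first administration of durvalumab until discharge from the hospital following surgical resection".
- **Sirolimus schedule (5.2.2).** A loading dose on day 1, "followed by 2mg orally daily from day 2 through 21". The synopsis puts the last dose one day before durvalumab cycle 1. Section 8.1.2 starts durvalumab on day 22, and the schedule of assessments allows 3 days either side.
- **Sirolimus criterion (6.3).** The DLT list includes "Delay in administration of scheduled doses of sirolimus greater than 2 weeks because of drug-related toxicity of any grade".
- **Onset (6.3).** "Any treatment-related toxicities that first occurred during the DLT period must be followed for resolution", to decide whether they qualify as DLTs. Nothing is said about events that begin earlier.
- **Consequence of the delay (6.4.2, Table 2).** "Patients requiring a delay of >2 weeks should go off protocol therapy".
- **Replacement (4.4).** "Patients who discontinue study treatment prematurely will not be replaced". Only patients who withdraw consent before durvalumab are replaced.
- **Halt rule (3.4).** The check is for "dose limiting toxicities (DLTs) related to sirolimus followed by durvalumab therapy". If at least 2 of 6 "patients have a DLT then additional enrollment will be halted until safety assessment is completed". Section 3.1 describes the check in the same terms.
- **DLT rate (11.2.1).** Patients with a DLT divided by total patients, with a Clopper-Pearson 95% interval. The denominator is not defined further.

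**The concern.** Safety of the regimen is a co-primary objective, and the 2-of-6 rule is the plan's only numerical safety trigger. Sections 3.1 and 3.4 aim it at the full sequence, and the DLT list contains a sirolimus criterion, so a reader would expect lead-in toxicity to count. The window in 6.3 opens after the sirolimus course has ended. The protocol's own sirolimus warnings (1.6.2.2) include non-infectious pneumonitis, and Grade 3 non-infectious pneumonitis is a listed DLT. If it began on day 15, the plan would not clearly count it. What is at stake is whether an early signal from the first drug can pause enrolment, and what the reported DLT rate measures.

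**Working it through.** **1. Plan's own figures.** The documents state no operating characteristics for the halt rule, so there is nothing to reproduce on this point. The pCR design is unaffected: exact two-stage power is 80.5% at 25% (stated as 80%), and exact type I error is 7.9% at 10% (limit 10%).

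**2. Can the delay criterion operate?**
- A delay covering more than 14 scheduled doses must start by day 7: days 7-21 hold 15 doses, days 8-21 hold 14. It has therefore run its length by day 21. The window opens on about day 22.
- With durvalumab at its earliest (day 19), at most 3 sirolimus days (19-21) overlap the window.
- If durvalumab instead waits for missed sirolimus doses, the delay again precedes the window.
- In each case Table 2 takes the patient off protocol therapy once the delay passes 2 weeks, so durvalumab should not follow.
- The exception needs durvalumab to be given while sirolimus is still on hold for toxicity, which departs from the planned sequence.

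**3. Chance of a halt.** Inputs, all assumed: *s* = probability of coming off protocol therapy in the lead-in for toxicity; *d* = probability of a DLT after durvalumab starts. Three readings of the per-patient DLT probability *p*:
- A. As written, six = first six enrolled (6.3): a lead-in loss keeps its place and cannot have a DLT, so p = (1 - s) × d.
- B. As written, six = those who reach surgery (a possible reading of 3.4 and 11.2.4): p = d.
- C. Window from day 1, every such lead-in stop counted as a DLT: p = 1 - (1 - s)(1 - d).

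P(halt) = P(at least 2 of 6) = 1 - (1 - p)^6 - 6p(1 - p)^5.

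| s | d | A: p, P(halt) | B: p, P(halt) | C: p, P(halt) |
|---|---|---|---|---|
| 1% | 10% | 0.099, 11.2% | 0.10, 11.4% | 0.109, 13.2% |
| 2% | 10% | 0.098, 11.0% | 0.10, 11.4% | 0.118, 15.1% |
| 5% | 5% | 0.0475, 3.0% | 0.05, 3.3% | 0.0975, 10.9% |
| 5% | 20% | 0.19, 32.0% | 0.20, 34.5% | 0.24, 44.2% |

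As *s* rises, A falls slightly, B is flat and C rises.

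**4. DLT rate.** Suppose one of the first six is lost in the lead-in to toxicity and one has a later DLT. The Clopper-Pearson limits are the 2.5% point of Beta(x, n - x + 1) and the 97.5% point of Beta(x + 1, n - x).
- As written, the rate could be 1/6 = 16.7% (0.4-64.1%) or 1/5 = 20.0% (0.5-71.6%), with no halt.
- Counted from day 1 it is 2/6 = 33.3% (4.3-77.7%), and enrolment pauses.

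**The case against.** **The durvalumab start may be deliberate.** Section 1.6.2 stresses that the risks of the combination are unknown and refers to DLT assessment of the combination portion. Section 6.3 ties its criteria to durvalumab-containing regimens. Sirolimus is approved, and 2 mg daily is the recommended dose in lymphangioleiomyomatosis (3.1). This stands as a plausible intention. It leaves the delay criterion without effect and 3.1 and 3.4 describing a wider check than 6.3 delivers.

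**Lead-in toxicity is probably uncommon.** In the head and neck study cited in 1.3, 16 patients took 15 mg and then 5 mg daily for 21 days, with one Grade 3 event. That stands, and it makes lead-in stop rates of 10-20% hard to defend. The contrasts at 1-5% are the relevant ones.

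**Other safeguards exist.** These are the planned safety assessment of the first six (11.2.4), monitoring committee review (12.5), AE summaries from the first sirolimus dose (11.1.1), sponsor termination (4.3) and individual holds (Table 2). All stand, but none sets a number for lead-in toxicity.

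**Stronger readings that the documents do not support.**
- *Section 6.3 excludes every lead-in event.* The onset sentence imposes follow-up on events that begin in the window. It does not say that earlier ones never count. Several criteria turn on failure to resolve within 30 days, so a Grade 3 event from day 15 could meet one around day 45. Its status is unclear.
- *Every lead-in stop bars durvalumab.* For Grade 4 stomatitis and other Grade 4 non-hematologic toxicity, Table 2 stops sirolimus without saying that protocol therapy ends.
- *More sirolimus toxicity makes a halt much less likely.* The fall is small on reading A and absent on reading B.

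**Conclusion.** The point holds as an internal inconsistency. The sirolimus-delay criterion has essentially no effect on the planned sequence. Toxicity with onset in the lead-in is not clearly counted in the halt rule or the DLT rate. Whether an event that persists into the window counts is left open. A patient taken off protocol therapy in the lead-in contributes no DLT on either reading of who the six are, so such losses cannot raise the chance of a halt.

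The size depends on assumed rates. At low lead-in toxicity the shortfall is about 2 to 4 percentage points (11.2% against 13.2%; 11.0% against 15.1%). At 5% lead-in stops and 20% later DLTs it is 10 to 12 points (34.5% or 32.0% against 44.2%). These comparisons assume that each lead-in stop ends protocol therapy and would count as a DLT from day 1. The inconsistency itself does not depend on the rates. The text should be corrected because it governs a stated safety rule.

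**What to change.** **Preferred.** In 6.3, start the DLT window at the first sirolimus dose, keep its end at hospital discharge, and keep the sirolimus-delay criterion. Define the six DLT-evaluable patients as those with at least one sirolimus dose who either had a DLT or were followed to discharge. Use that set as the denominator in 11.2.1.

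**If only the period after durvalumab is intended.** Delete the sirolimus-delay criterion and report lead-in toxicity stops among the first six at the 11.2.4 safety assessment.

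**Cost.** A few lines in 6.3 and 11.2.1, or in 6.3 and 11.2.4. No new data are needed, since 10.4 already collects AEs from consent with dates and grades. The preferred change makes a pause more likely for a tolerable regimen: 3.0% to 10.9% at assumed rates of 5% and 5% (reading A against C). A halt only suspends new enrolment until safety review, and under 6.3 patients already on therapy continue.
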